Objectives:	
The primary objectives are to evaluate the safety and tolerability of the drug in subjects with mild Alzheimer's disease dementia, as assessed through regular clinical evaluations throughout the dosing period. Critically, eventual treatment-emergent toxicities will drive our decision process to pursue or stop dosing. The secondary objective is to determine drug effect on relative annual brain atrophy rates in the two groups by comparing pre- and post-exposure volumetric MRI data. Tertiary objectives will be evaluated through the utilization of cognitive assessments throughout study.
 
The study design will support two exploratory objectives using blood, CSF, and saliva biospecimen collection from subjects with mild AD dementia. Blood and CSF samples will be analyzed for AD biomarkers (amyloid beta, tau, and p-tau)

	as well as CSF inflammatory markers. Saliva samples will be assessed for amyloid-beta biomarkers (primarily Aβ40 and Aβ42), which may serve as dynamic surrogate markers of therapeutic drug efficacy.
Endpoints:	
Primary Endpoint: Safety to be evaluated through reported adverse events (AEs), clinical laboratory tests (hematology, and serum chemistry,), vital signs, physical and neurological examinations, and electrocardiograms (EKGs).
 
Secondary Endpoints: Change in rates of neurodegeneration as measured with volumetric MRI.
 
Tertiary Endpoint: Cognitive changes throughout duration of the study to be evaluated through cognitive assessments, including, ADCOMS (with ADAS-Cog13, MMSE, CDR-SOB as source measures)
 
Exploratory: ADCS-ADL + CSF/blood/saliva biomarkers

Study Population:	105 male and female outpatients, 50-85 years of age, diagnosed with early/mild Alzheimer's disease dementia primarily residing in Phoenix, AZ and greater surrounding areas. Because of the local demographics, the study population will mostly consist of Caucasians, although all efforts will be made to enroll other ethnicities.

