12. STATISTICAL CONSIDERATIONS

STATISTICAL HYPOTHESES

- Primary and Exploratory Efficacy Endpoint(s):

The null hypothesis for the primary efficacy endpoint is that biomarker measures (primary endpoint: vMRI; tertiary and exploratory endpoints: CSF biomarkers, blood inflammatory markers, saliva amyloid beta levels) will be the same in Siponimod- vs. placebo-treated study subjects after 12 months (end of dosing).

The alternative hypothesis is that Siponimod will improve biomarker measures at the same time point.

- Secondary Efficacy Endpoint(s):

The null hypothesis for the secondary efficacy endpoint is that cognitive measures (ADCOMS) will be the same in Siponimod - vs. placebo-treated study subjects after 12 (end of dosing) and 18 months (6 months follow up).

The alternative hypothesis is that Siponimod will improve cognitive measures at the same time points.

SAMPLE SIZE DETERMINATION

Mild AD subjects will receive an escalating dose of Siponimod up to 1 mg/day (N=70) or placebo (N=35) for 12 months (Table 2). We conducted a power analysis for sample size determination using the reported data from brain volume changes in SPMS subjects treated for at least 12 months with Siponimod or placebo²⁵. We wished to fit a repeated measures ANOVA model with two treatment levels in drug vs. placebo, and 4-time measures to receiving the drug (i.e. vMRI at baseline, 6, 12, and 18 months). We defined $Y_{ij} = \mu + \alpha_i + \tau_j + (\alpha\tau)_{ij} + \varepsilon_{ijk}$, where Y_{ijk} denotes the measure on brain atrophy, α_i denotes the treatment effect $i = 1, 2$; τ_j denotes the time effect at time $j=1, 2, 3, 4$; $k = 1, n$; $(\alpha\tau)_{ij}$ is the interaction between time and treatment; and ε_{ijk} is the error term²¹. We study the effect of the drug on brain atrophy. The between-subject factor in our model is treatment, with two levels (study drug and placebo), and we allocate each treatment in the ratio 2:1. The within-subject factor is time, with four levels (0, 6, 12, and 18 months). The number of patients needed is determined to achieve a power of 0.90 at significance level $\alpha = 0.05$ for the test of the interaction between time and treatment, where the contrast over time contains all pairwise comparisons. We also intend to generate a plot of power versus sample size that covers the power range of 0.05 to 0.90.

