The default Hotelling-Lawley F test is appropriate for this study, especially because it is the same as the Wald test in PROC MIXED with the DDFM=KR Kenward-Roger degrees-of-freedom method and an unstructured covariance model. We conjecture that the mean measure of brain atrophy will decrease by 20-30% (GLMPOWER Procedure SAS/STAT User's Guide 9.2). To characterize the variability, we specify a set of parameters that defines the entire covariance matrix of the residuals. We conjecture that the error standard deviation is the same at all four time points, with a value approximately 4-11, and we account for uncertainty by including both the lower and upper ends of this range in the sample size analysis. The power analysis is given in Table 1. A power of 90% is obtained with 90-95 subjects to determine a difference in brain atrophy over placebo. To account for a possible ~10% attrition rate, we will use 105 subjects in total.

Table 4: Power Analysis Versus Sample Size.

Index	Transformation	Effect	Actual Power	N Total
1	Time	Time	0.903	90
2	Mean (Dep)	Treatment	0.906	94

We chose to study mild AD subjects for the major reason that these patients do suffer continuous but limited/slow brain atrophy, which is measurable by vMRI²², vs. mild cognitive impairment patients (MCI), whose brain atrophy may not progress enough on an annual basis for robust quantification. Furthermore, the functional disabilities in mild AD patients are not too pronounced yet vs. moderate and severe AD. Thus, if Siponimod is able to slow down brain atrophy, mild AD subjects will likely benefit the most by, hopefully, also slowing down functional decline.

POPULATIONS FOR ANALYSES

All subjects receiving at least 1 dose of study drug will be included in the safety analyses. For efficacy analyses, subjects will be included only if they reach Visit 12 (Week 8) of the dosing period (i.e., patients withdrawn before Visit 12 and replaced will not be included in this efficacy analysis). Patients withdrawing or withdrawn from the study before Visit 12 are unlikely to demonstrate a change in the biomarkers investigated here (cognitive performance) given the effects of Siponimod in the CNS take several weeks to be measurable.

STATISTICAL ANALYSES

GENERAL APPROACH

All intra and inter-subject outcome measures collected during our study will be sent to [name] at Arizona State University for statistical processing.

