The data will be summarized using professional standards. The distributions of patients completing each study visit and the reason for early terminations will be tabulated for each treatment group. The duration of double-blind treatment within each treatment group and compliance rates will be summarized by descriptive statistics (mean, standard error, standard deviation, median, minimum, maximum and sample size) for days of treatment and for total days of exposure and by the distributions of patients exposed to various durations of treatment categories. Demographic and baseline characteristics will be summarized by descriptive statistics for all patients in each treatment group.

Volumetric MRI data measures will be computed to determine eventual brain volume changes between pre- and post-treatment, which will validate or refute our central hypothesis. Data from Aims 2-3 will also be used in correlational analyses for blood vs. AD central markers to investigate whether minimally invasive tests that use peripheral markers could be used as proxies to track drug performance. We wish to fit a repeated measures ANOVA model with two treatment levels (drug and placebo) and 13 time measures (for blood markers). We define $Y_{ij} = \mu + \alpha_i + \tau_j + \varepsilon_{ijk}$, where Y_{ij} denotes the measure on siponimod, α_i denotes the treatment effect $i=1,2$, τ_j denotes the random effect at subject $j=1, 2, \dots, 70$, $k=1, \dots, 13$ and ε_{ijk} is the error term. We assume that the random effect is distributed with mean zero and σ^2 . Paired data tests will be used to assess eventual biomarker changes between pre- and post-dosing datasets. Correlational statistics and linear regressions will be employed to determine possible dose-response for siponimod on the biomarkers investigated. If siponimod has an effect on inflammatory and AD biomarkers (either in blood, or in CSF), the current study should demonstrate an amelioration of these biomarker profiles. Also, we will use the results of cognitive tests to calculate the average conversion rate, continuous variables, and time to event analysis in our two groups.

Missing data will not be imputed, and all summary statistics will be reported based upon observed data. For limited analyses where formal inferential analyses are specified, rank-based methods will be used to incorporate subjects missing follow-up assessments.

ANALYSIS OF THE PRIMARY EFFICACY ENDPOINT(S)

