Statistical analysis of the biomarkers and clinical assessments will be carried out by our biostatistician. Comparisons will assess the change from baseline for the following markers assessed at the frequency indicated in the schedule of visits Table 1):

- vMRI, which is used to estimate the annual rate of brain atrophy.

ANALYSIS OF THE SECONDARY ENDPOINT(S)

Statistical analysis of the biomarkers and clinical assessments will be carried out by our biostatistician. Comparisons will assess the change from baseline for the following markers assessed at the frequency indicated in the schedule of visits Table 1):

- Alzheimer's Disease Assessment Scale - Cognitive (ADAS-Cog13);
- Clinical Dementia Rating-Sum of Boxes (CDR-SOB);
- Mini Mental State Examination (MMSE);
- ADCOMS, which is calculated using components of the three cognitive tests indicated above.

SAFETY ANALYSES

- Concomitant Medications

Concomitant medications will be coded by the World Health Organization (WHO) Drug Dictionary and tabulated by the treatment group.

- Adverse Events

The incidence of all treatment-emergent AEs (TEAEs) and treatment-related AEs will be tabulated by treatment received. These AEs will be classified by system organ class and preferred term using the Medical Dictionary for Regulatory Activities (MedDRA). For incidence reporting, if a subject reported more than one AE that was coded to the same system organ class or preferred term, the subject will be counted only once for that specific system organ class or preferred term. A TEAE is defined as an event that first occurs or worsens in intensity after the administration of study drug. Events recorded between the time the informed consent is signed and the first study drug administration will be listed.

An overview of AEs, which includes subject incidence of TEAEs, treatment-related AEs, SAEs, deaths, and AEs leading to discontinuation, will be presented. For AEs presented by severity, the worst severity during the study will be presented for each subject.

The subject incidence of TEAEs and treatment-related AEs will be summarized by system organ class and preferred term.

- Serious Adverse Events

All SAEs will be listed and summarized in a similar manner to AEs.

- Clinical Laboratory Results

Clinical laboratory values will be measured by a central laboratory.

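### The vMRI hypothesis is set at 12 months, but the stated 90% power is for an interaction that includes the off-drug Month 18 scan, and Table 4 shows power for neither; some baseline scans may also follow the first dose

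*Protocol*

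**What the plan says.** **Hypothesis.** Section 12, Statistical Hypotheses, states the null for vMRI as measures that "will be the same in Siponimod- vs. placebo-treated study subjects after 12 months (end of dosing"). The alternative is at the same time point. Month 18 is added only in the next item, for ADCOMS.

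**Powered test.** Section 12, Sample Size Determination, describes a repeated-measures model with scans at baseline and Months 6, 12 and 18: "The within-subject factor is time, with four levels (0, 6, 12, and 18 months"). The 90% power is "for the test of the interaction between time and treatment, where the contrast over time contains all pairwise comparisons". On variability it says: "We conjecture that the error standard deviation is the same at all four time points". No correlations between scans and no profile of the effect over time are given.

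**Result.** "A power of 90% is obtained with 90-95 subjects to determine a difference in brain atrophy over placebo". Table 4 lists two effects: Time, power 0.903 at N=90, and Treatment on the mean of the scans, power 0.906 at N=94. There is no interaction row and no Month 12 row.

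**Other wording on vMRI.** The synopsis aims to "determine drug effect on relative annual brain atrophy rates in the two groups by comparing pre- and post-exposure volumetric MRI data". General Approach refers to "brain volume changes between pre- and post-treatment, which will validate or refute our central hypothesis". Analysis of the Primary Efficacy Endpoint(s) says: "Comparisons will assess the change from baseline for the following markers assessed at the frequency indicated in the schedule of visits". None of these names a visit.

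**Scan timing.** Section 1.1 gives the first dose at the Baseline Visit (24 to 48 hours later after a lumbar puncture). It allows the vMRI a window of plus four weeks if none was done at screening, and footnote o of the Schedule of Events repeats a four-week window. A vMRI before the Baseline Visit is required only when no MRI or CT exists from the past 12 months. The eye exam is marked as pre-dose; the vMRI is not. Section 10 nevertheless calls this scan Baseline (Week 0).

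**The concern.** A power statement is useful only if it belongs to the test of the stated hypothesis. Here the hypothesis concerns the end of dosing, the sample-size text powers a joint test that also draws on a scan six months off drug, and the table that should show the result covers two other effects. A reader cannot tell what chance 105 participants give of detecting an on-treatment difference at Month 12, which Section 10 treats as the main efficacy question. The interaction also answers a different question: the arms could part, or come back together, during washout and so affect the result without bearing on Month 12.

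The scan window is a smaller, separate matter. A scan taken after dosing has begun no longer measures the pre-treatment state, and the exposed interval up to Month 12 becomes shorter for those participants.

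**Working it through.** **1. The plan's own figures.** The attrition step reproduces: 94/0.9 = 104.4, rounded up to 105 (the Time row would give 90/0.9 = 100). In reverse, 105 × 0.9 = 94.5, or about 94 completers, 63:31 at 2:1. The 90 and 94 themselves cannot be reproduced, because the baseline mean, the effect at each visit and the correlations are missing.

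**2. What each effect tests.** Let g0, g6, g12 and g18 be the between-arm gaps at the four scans.
- Hypothesis: g12 − g0 (1 df).
- Interaction: all changes in the gap jointly (3 df). The pairwise comparisons include 0 versus 12 months, but only inside the joint test.
- Treatment row: the average of all four gaps, including baseline and Month 18.
- Time row: not a between-arm comparison.

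**3. Illustration.** Taken from the protocol: 63:31 completers, equal SDs, alpha 0.05. Assumed: compound symmetry or AR(1), correlation 0.50 to 0.98. Power uses the noncentral F with λ = [63 × 31/94] × d′S⁻¹d, where d is the vector of tested gaps and S its per-subject covariance; 63 × 31/94 = 20.78.

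A Month 12 gap of 0.719 SD of change gives λ = 20.78 × 0.719² = 10.74 and 90% power with 1 and 92 df. This effect is back-solved, not a protocol figure. Let the gap grow linearly to Month 12. Under compound symmetry the interaction has λ = 10.74 × 2 × Σ(g − mean g)², with g scaled to 1 at Month 12, tested with 3 and 90 df.

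| Month 18 gap | Scaled gaps | Σ | λ | Power, compound symmetry | Power, AR(1) |
|---|---|---|---|---|---|
| held | 0, 0.5, 1, 1 | 0.6875 | 14.77 | 90% | 77-82% |
| half lost | 0, 0.5, 1, 0.5 | 0.5 | 10.74 | 77% | 82-92% |
| all lost | 0, 0.5, 1, 0 | 0.6875 | 14.77 | 90% | 97-100% |
| widens | 0, 0.5, 1, 1.5 | 1.25 | 26.85 | 99% | 93-97% |

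The interaction's power thus runs from 77% to about 100%, on either side of 90%, depending on the washout and the correlations.

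Averaged Treatment contrast in the same setting: 7-93% if the gap is held and 6-55% if it is lost, lowest at high correlation. One case, compound symmetry 0.8, gap held: the mean gap is 0.625 of the Month 12 gap, the variance of a four-scan mean is (1 + 3 × 0.8)/4 = 0.85, and λ = 20.78 × (0.719² × 0.4 × 0.625²)/0.85 = 1.97, which gives about 28% power.

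**4. Can the interaction reject with no Month 12 difference?** Take arms that are equal through Month 12 and differ at Month 18 by 0.1, 0.2 or 0.3 SD of change. The interaction rejects in 7-9%, 13-22% or 25-46% of trials, against 5% for a Month 12 contrast. The protocol does not predict this pattern; it only shows what a rejection can mean.

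**5. Scan window.** Day 1 to Day 364 is 363 days, and a baseline scan 28 days late leaves out 28/363 = 7.7% of exposure days. This applies only to participants without a screening vMRI.

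**The case against.** Four points on the other side carry weight.

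- The protocol already fixes the measure, the comparison and the 12-month time point. Naming the exact contrast is ordinary SAP content, and the SAP is not shown. A reader might infer that no Month 12 test is planned. The document does not support that. What remains is a mismatch inside the protocol between its hypothesis and its power statement.
- The interaction appears only in the sample-size text. The efficacy analysis section speaks of change from baseline and does not adopt it. A reader might infer that a difference seen only at Month 18 would be declared as on-treatment benefit. That would need a decision rule the protocol does not state.
- The illustrations rest on assumed correlations and time profiles, and the interaction's power can be higher as well as lower. They do not show that the trial is underpowered. This stands in full.
- The late baseline scan is minor. The endpoint is an annual rate, and annualising on actual dates removes the bias if the slope difference is constant. The window is the same in both blinded arms. On the nominal titration schedule the first 28 days carry only 11 of 342.75 mg, about 3% of the cumulative dose. This too stands, but the protocol does not say that actual dates will be used, and the label Week 0 conflicts with the window.

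**Conclusion.** The point holds in a limited form. The stated 90% power belongs to an interaction that includes the off-drug scan, Table 4 displays neither that interaction nor the Month 12 contrast, and so the power for the stated vMRI hypothesis is not shown. That conclusion rests on the text alone. Its numerical size does not: with equal SDs and assumed correlations of 0.50 to 0.98, the interaction has about 77-100% power where the Month 12 contrast has 90%, and the averaged Treatment contrast behind N=94 anywhere from 6% to 93% for gaps held or fully lost off drug. None of these ranges is a corrected power for this trial.

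The baseline window is a modest attenuation, at most 7.7% of exposure days in a subset. A reader might infer that a post-dose baseline could favour the drug; with the same window in both blinded arms it creates no false-positive bias.

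vMRI is the secondary objective. The primary objective of safety and tolerability is untouched. The change should be made, but it does not put the design in doubt.

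**What to change.** - Keep the mixed model. Name one vMRI decision test: the between-arm difference in baseline-to-Month-12 atrophy, annualised on actual scan dates.
- Report Month 18 separately as an off-drug estimate.
- Restate the power that 105 participants (about 94 completers) give for that contrast, with the assumed effect, SD with units, and correlations written out. N need not change.
- Require the baseline vMRI before the first dose, as is already done for the eye exam, and align the Baseline Visit text, footnote o and Section 10.

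Cost: wording in the protocol and SAP and one re-run of the power calculation, with no added visits or scans. The first dose may occasionally have to wait for a scan slot, and the restated power may be less favourable than 90%.

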Immuno-modulation is mostly achieved by preventing egression of lymphocytes from lymphoid organs, and the modulation of cytokine expression, including microglia⁵. For T lymphocytes, it was shown that S1PR modulators prevent the infiltration of CD8+ memory cells in the central nervous system (CNS). This property could be key for AD since, very recently, the group of Wyss-Coray showed that CD8+ T cells likely play a critical role in the adaptive immune response in the CNS of AD patients^{17,42}. On the other hand, the molecular mechanisms for neuroprotection are currently poorly understood. Nonetheless, both fingolimod and Siponimod lower the rate of brain atrophy in remitting relapsing MS (RRMS)⁷. Very interestingly, Siponimod was found to reduce brain atrophy at later stages of MS called secondary progressive MS (SPMS), making it the first drug with a demonstrated neuroprotective effect in SPMS¹². More precisely, at month 12 the percentage of total brain volume change from baseline adjusted mean were -0.28% and -0.46% ($p < 0.0001$) in Siponimod vs placebo-treated SPMS subjects, respectively²⁵.

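### The stated 90% power with 90-95 subjects does not follow from the inputs the protocol gives, and one N per row cannot cover an error SD of 4 to 11

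*Protocol*

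**What the plan says.** All of this is in protocol section 12, Sample Size Determination, unless noted.

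- **Source of the inputs.** The power analysis was done "using the reported data from brain volume changes in SPMS subjects treated for at least 12 months". Section 2.2 (and again section 3.1.2) gives that trial's month-12 result: "percentage of total brain volume change from baseline adjusted mean were -0.28% and -0.46" percent, siponimod against placebo.
- **Test and target.** "The number of patients needed is determined to achieve a power of 0.90 at significance level" 0.05, "for the test of the interaction between time and treatment, where the contrast over time contains all pairwise comparisons". The four times are 0, 6, 12 and 18 months.
- **Allocation.** "we allocate each treatment in the ratio 2:1".
- **Effect.** A conjectured 20-30% decrease in the mean atrophy measure. No reference mean and no unit are given.
- **Variability.** One error SD at all four times, "with a value approximately 4-11, and we account for uncertainty by including both the lower and upper ends of this range". No unit is given. The text says the whole residual covariance matrix was specified, but it states no correlation.
- **Result.** The power table has two rows: Time (power 0.903, N=90) and Treatment (power 0.906, N=94). The text concludes 90% power with 90-95 subjects, and 105 after about 10% attrition (70 and 35).

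**The concern.** The section names a data source and then uses numbers that cannot be traced to it. An SD of 4-11 is about 9 to 24 times the whole placebo change of 0.46 reported from the cited trial (4/0.46 = 8.7; 11/0.46 = 23.9), so it is hard to see effect and SD as being on one scale. The SD range is wide, yet each table row gives a single N.

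The 90% figure is the only stated justification for N=105. The General Approach part of section 12 says the brain-volume result is to decide the central hypothesis. If the power is unsupported, a null vMRI result could be read as strong evidence against the drug when the trial may have had little chance of seeing the effect.

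**Working it through.** **Inputs from the protocol.** α = 0.05, taken as two-sided because the F test has no direction; target power 0.90; allocation 2:1; N = 90 and 94; SD 4 to 11; cited difference 0.46 - 0.28 = 0.18 points; conjectured decrease 20-30%. Assumed here because not stated: SD in percentage points, compound symmetry, and the time profile of the difference.

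**1. What reproduces.** Attrition: 94/0.9 = 104.4, rounded up to 105. The N of 90 or 94 itself did not reproduce under any reading tried.

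**2. Two-group comparison, noncentral t, N = 94 as 63:31.** Noncentrality = d × √(63×31/94) = d × 4.558, with 92 degrees of freedom.

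| Difference | d at SD 4 | Power | d at SD 11 | Power |
|---|---|---|---|---|
| 0.18 (cited trial) | 0.045 | 5.5% | 0.016 | 5.1% |
| 0.092 (20% of 0.46) | 0.023 | 5.1% | 0.008 | 5.0% |
| 0.138 (30% of 0.46) | 0.035 | 5.3% | 0.013 | 5.0% |
| 0.46 (all placebo loss) | 0.115 | 8.1% | 0.042 | 5.4% |

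In reverse, power 0.906 at 63:31 needs d of about 0.73. That is a difference of 0.726×4 = 2.9 at SD 4 or 0.726×11 = 8.0 at SD 11. For a difference of 0.18 it needs an SD of 0.18/0.726 = 0.25. Reading 20-30 as absolute units goes to the other extreme: only about 3-15 patients would be needed.

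**3. Time-by-treatment test (Hotelling-Lawley, 3 df), N = 90 as 60:30.** Under compound symmetry, with d_j the group difference at time j,

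λ = (60×30/90) × Σ(d_j - mean d)² / [SD² × (1 - ρ)].

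With an assumed profile of 0, 0.09, 0.18, 0.18 the sum of squares is 0.022275. At SD 4, λ = 20×0.022275/16/(1 - ρ) = 0.0278/(1 - ρ).

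| ρ | Power, SD 4 | Power, SD 11 |
|---|---|---|
| 0 | 5.2% | 5.0% |
| 0.5 | 5.3% | 5.0% |
| 0.9 | 6.6% | 5.2% |
| 0.99 | 24.6% | 7.2% |
| 0.998 | 87.9% | 17.3% |

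Power of 90% needs λ of about 14.83, so 1 - ρ = 0.0278/14.83 = 0.0019, or ρ of about 0.998 at SD 4. At SD 11, 20×0.022275/121 = 0.00368 and 1 - ρ = 0.00025, or ρ of about 0.9998.

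If the difference instead grows to 0.27 at month 18 (sum of squares 0.0405), power is 8.0% (SD 4) or 5.4% (SD 11) at ρ = 0.9, and 43% or 9% at ρ = 0.99. At SD 4, 90% then needs 1 - ρ = 0.0506/14.83 = 0.0034, or ρ of about 0.997.

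**4. Check that needs no unit.** At a fixed effect and correlation, N scales with SD²: (11/4)² = 7.56, so the two ends of the range differ about 7.6-fold in N. At fixed N, d = 0.726 at SD 4 becomes 0.726×4/11 = 0.264 at SD 11, and power falls from 90.6% to about 22%. The 3-df test behaves alike: λ = 14.98 (power 0.903) becomes 14.98×(4/11)² = 1.98, with power about 18%.

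**5. Allocation.** 94/3 = 31.33, so 94 does not split exactly 2:1; the nearest totals that do are 93 and 96. 90 (60:30) and 105 (70:35) do split.

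**The case against.** **The unit match is an assumption.** If the SD is on another scale, dividing 0.18 by it means nothing. The model itself points that way: baseline is one of the four times and carries the same SD, whereas percent change from baseline is zero for everyone at baseline. This stands. The 5% figures are conditional, and a reader who inferred that the trial truly has 5% power would go beyond the documents.

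**0.18 is not the effect written into the power section.** That effect is a 20-30% decrease from an unstated mean. It would give about 90% power wherever the mean is about 2.4 to 3.6 times the SD (0.726/0.30 and 0.726/0.20): a mean of 9.7-14.5 at SD 4, or 27-40 at SD 11. This stands as a possibility, but the protocol reports no atrophy measure with such a mean and ties the inputs to the MS trial's brain-volume data.

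**A t test is not the planned analysis.** True, so step 3 runs the planned interaction test. A high enough correlation does rescue the power, but only at values near 0.998 or above (0.997 with the growing profile), and the protocol states none.

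**N=94 is trivial.** Largely right. 63:31 is 2.03:1, and 90 and 105 split exactly. A reader might infer that a 1:1 calculation was run; one integer cannot establish that, and no power or sample size should be derived from it.

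**Table 4 may have been sized at SD 11.** Then one N would be conservative for SD 4. The text does not say so.

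**vMRI is the secondary objective.** The primary is safety and tolerability, and the remedy adds no patients. That limits the consequence; it does not support the 90%.

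**Conclusion.** The stated power of 90% with 90-95 subjects is not supported by the protocol's own inputs. Effect and SD are not shown on a common scale, and the reference mean and within-subject correlation are missing. The power table also has no row for the interaction test the size is said to be set for.

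Conditional on the SD being in percentage points, the cited 0.18 gives about 5% power in a two-group comparison. The time-by-treatment test gives about 5-7% up to a correlation of 0.9 under the plateau profile (up to 8% if the difference keeps growing).

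Independent of any unit, one N per row cannot represent both SD ends at a fixed effect and correlation: 90.6% at SD 4 is about 22% at SD 11. This is the firmest part of the point.

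The documents do not show what the true power is, that N=105 is the wrong size, or that 1:1 weights were used. The uneven split of 94 is only a minor further sign that the tabulated calculation does not match the design described.

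**What to change.** Re-run the calculation in section 12 for the time-by-treatment test it names, at 2:1 and about 63:31 evaluable (105×0.9 = 94.5). State effect, SD and within-subject correlation on the vMRI endpoint's own scale, say where each comes from, and show power at both ends of the SD range.

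Replace the 90% statement by the resulting power. Alternatively, state the detectable difference: about 0.73 SD for a two-group comparison at 63:31 (0.72 for exactly 90%). Keep N=105.

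The cost is a new calculation and revised wording in one section. The stated power will probably be less favourable; no patients, visits or scans are added.
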